8.4. Subject Numbers

Subjects will be screened, and if eligible, enrolled and eventually randomized for the study. All screened subjects will be entered in the EDC. As each subject is added to the EDC system, they will be assigned a Screening number, which will consist of a unique 2-digit site code (starting with 01) and a unique 2-digit sequential number (starting with 01 at each site) indicating the sequence at which the subject was screened for eligibility. This Screening number will remain with the subject through enrollment and randomization, and will be considered their Subject identification (ID) if randomized into the study.

Subjects will be eligible for rescreening. Once laboratory results are obtained and a final determination of eligibility is made, subjects will be contacted to schedule the first treatment visit. While immediate re-testing of laboratory results is not allowed, subjects failing to meet laboratory-based eligibility criteria may be rescreened for laboratory-based eligibility after a 30 day wait. If this occurs, the subject will maintain the same Screening number, but will have all eligibility reviewed and reconfirmed prior to enrollment.

9. STUDY TREATMENTS

9.1. Allocation to Treatment

Subjects will be randomly assigned to one of the two treatment sequences to receive the blinded study drug (see [Table 3](#)). A total of 122 subjects will be randomized, with a goal of having an approximately equal number of subjects randomized to each of the two treatment sequences. If there are subjects who are enrolled, but fail to be randomized, compensatory enrollment may be utilized to achieve at least 122 subjects who are randomized for the study. Once a subject is randomized, the subject will be analyzed for the study. Each subject will receive a single SC injection to the abdomen around the umbilicus on each of the two treatment days, with a period of 7 to 28 days between treatment 1 and treatment 2.

9.2. Blinding

For this study, the subject but not the Investigator will be blinded (single-blind design). The G-Pen 1 mg device makes a series of two audible clicks when the dose is administered. To help ensure blinding, the subject will wear headphones that play music to mask sound during dosing procedures. The subject's ability to see the injection equipment and procedure will be obstructed by use of a blindfold placed prior to dosing. The subject will be instructed not to talk with the study staff about their impression of which product he/she received at a visit until the end of the second treatment sequence. At which time, the subject will be asked to guess what their first treatment was, and what their second treatment was from the choices of "Xeris Glucagon, G-Pen, administered by auto-injector" or "Comparator Glucagon, GlucaGen Hypokit, administered by needle and syringe". The subject's responses will be recorded in the electronic Case Report Form (eCRF) for the Subject Study Drug Assignment Questionnaire (see [Appendix 5](#)).

In the event that a subject is inadvertently unblinded during one or both of the treatment sequences, the investigator will note the event as a protocol violation, and the subject will be allowed to continue further study treatments as per the protocol.

9.3. Drug Supplies

9.3.1. Drug Product Formulation and Packaging

Xeris G-Pen is a non-aqueous, injectable liquid formulation of glucagon. The G-Pen drug product consists of 1 mg synthetic glucagon peptide dissolved in a primary DMSO solvent, with trehalose added as a stabilizing excipient. G-Pen drug product is filled into West Pharmaceutical's 1 mL long Crystal Zenith[®] cyclic olefin polymer (plastic) pre-filled syringe with a Flurotec[®] coated plunger. The pre-filled syringe is loaded into an SHL Molly[®] single-use, disposable auto-injector, and packaged in a sealed poly/foil pouch. The drug product is stored at controlled room temperature (20 to 25°C [68° to 77°F]) prior to use.

The G-Pen drug product is manufactured under current GMP by Pyramid Laboratories, Inc. (Costa Mesa, CA), and packaged under current GMP by SHL Group (Deerfield Beach, FL), both contract manufacturers for Xeris.

9.3.2. GlucaGen Hypokit for Injection

GlucaGen Hypokit (Novo Nordisk) will be purchased commercially and provided by Xeris. The glucagon will be stored at the CRC pharmacy according to labeled storage conditions.

9.3.3. Preparation, Dispensing and Administration

G-Pen will be supplied as 0.2 mL of non-aqueous solution in a plastic Crystal Zenith 1 mL long syringe loaded into a Molly disposable AI. Subcutaneous administration will be performed by a qualified CRC staff member who has read the written Instructions for Use provided by Xeris.

In the case of GlucaGen Hypokit, a new vial of lyophilized glucagon will be fully reconstituted immediately prior to abdominal administration using 1 mL of sterile diluent provided in the commercial kit as per the GlucaGen Hypokit Summary of Product Characteristics (SmPC) and Prescribing Instructions [[Novo Hypokit](#)].

Study drug will be administered according to the randomization schedule accessed in the EDC system (see 8.3). Randomization will occur at the start of the induction procedure, or about 2 to 3 hours prior to administration of study drug. When the Investigator believes the hypoglycemia induction procedure is approximately 1 hour from completion, a member of the study team will deliver the correct investigational product (IP) for the visit to the clinic area, making sure to maintain subject blinding.

The study drugs will not be prepared ahead of time. Instead, preparation of the investigational product (IP) (i.e., re-constitution of GlucaGen Hypokit) will begin *after* the confirmatory plasma glucose reading is obtained, indicating that a hypoglycemic steady state has been achieved, i.e., upon a “decision to dose.”

G-Pen is being developed for SC injection. The marketed comparator is labeled for both SC and intramuscular (IM) injection. Both products will be administered via the SC route to the abdomen, around the umbilicus.

The G-Pen auto-injector is made to be pressed against the skin perpendicularly (i.e., at a 90° angle) to the injection site. The injection technique for G-Pen will follow printed instructions for use (IFU) provided by Xeris.

For GlucaGen Hypokit, the skin should be pinched to avoid an IM injection. The needle will be inserted into the loose tissue under the injection site at a 90° angle and the product injected smoothly over 1 to 3 seconds. Following injection, light pressure should be applied to the injection site, as the needle is withdrawn.

Prior to administration of the study drugs, the intended injection site should be sterilized with an alcohol wipe and examined to ensure it has a normal appearance and is free from signs of inflammation or injury. The site staff will document the administration act (i.e. location, study product/dose) in the Vision EDC system.

9.3.4. Drug Storage and Drug Accountability

Unless notified otherwise by the Sponsor, all supplied G-Pen auto-injectors and GlucaGen Hypokit kits are to be stored at controlled room temperature (20°C to 25°C [68° to 77°F]). Excursions between 15° and 30° C (59° and 86 °F) that are experienced in pharmacies, hospitals,

and warehouses, and during shipping are allowed. Drug solution should be clear and of a water-like consistency at time of use.

The Investigator or an approved member of the study staff will ensure that the study drugs are stored in a secure area under recommended storage conditions and in accordance with applicable regulatory requirements.

The site will maintain appropriate documentation of continuous storage conditions and these records will be monitored in an on-going basis by the monitor. Any deviations in the storage conditions must be documented (including minimum and maximum temperature excursion as well as estimate of total duration of storage outside the recommended storage conditions). Such deviations must be communicated to the Sponsor as soon as identified by the site with an appropriate course of action taken, regarding the future use of the study drugs, upon consultation with Xeris.

After administration, used vials of GlucaGen Hypokit should be returned to the kit and stored for accountability, while the syringe is disposed as per each site's standard practice. Used G-Pens should be returned to the foil pouch, which will be sealed with tape, and stored for accountability. Any devices that fail to function should be handled in a similar manner, but they should also be identified on the pouch label as a failure. Disposal of the study products should occur away from the subject in a manner that ensures blinding.

The Investigator must maintain adequate records documenting the receipt, use, loss or other disposition of the investigational drug products and supplies. Unused G-Pens and Novo GlucaGen Hypokits will be returned to Xeris. Used G-Pen auto-injectors will be returned to Xeris after accountability is performed during site close-out. Used GlucaGen Hypokits and other used supplies, will be destroyed according to local regulation and applicable Xeris standard operating procedures (SOPs), following accountability by Xeris or its designee.

9.4. Concomitant Medications

All subjects must be questioned about concomitant medications at each visit. Medications taken within 4 weeks before Day 1 will be documented in the eCRF. Any changes to a subject's concomitant medication regimen after the first treatment on Day 1 will also be documented in the eCRF.

Except for those medications (e.g., warfarin) listed under the exclusion criteria (see Section 8.2) and other current investigational agents which are absolutely proscribed, there are no medications that are specifically prohibited during participation in the study. Subjects should be on a stable dose of all concomitant medications for at least 30 days prior to Screening, and they will be encouraged to avoid making changes to their concomitant medication regimen during participation in the study. In addition, Investigators are encouraged to avoid adding to or changing a subject's medications during study participation unless deemed medically necessary.

10. STUDY PROCEDURES

A schedule of assessments for this study is provided below in [Table 5](#).

10.1. Visit 1 – Screening (Day -30 to -3)

Subjects will be screened to confirm they meet the inclusion/exclusion criteria for the study. Prior to completing any screening activities, the Investigator or study team member will obtain informed consent from each subject in accordance with the procedures described in [Section 16.3](#). A copy of the consent/authorization form will be given each subject. The original will be kept by the site for the source document.

Subjects will be instructed to complete a Screening Visit at least 3 days (to allow for receipt of blood test results), and no more than 30 days prior to the anticipated date of the first Treatment Visit (Day 1). The following evaluations will be completed during the Screening Visit to confirm subjects meet eligibility criteria for this study:

1. Assessment of inclusion/exclusion criteria by a study investigator, including a review of the subject's medical history and medications.
2. Recording of the subject's insulin correction factor (i.e., the reduction in blood glucose in mg/dL per 1 unit of insulin taken).
3. Measurement of height and weight (no shoes, lightly clothed).
4. Physical examination, excluding breast, pelvic, and genitourinary exams.
5. Performance of a 12-lead ECG after the subject has completed a 5-minute supine rest.
6. Assessment of vital signs, including measurement of BP, after a 5-minute seated rest.
7. Urine drug screen. Note: At the Investigator's discretion, subjects with a positive result will be allowed to participate if the subject reports use of a concomitant medication that explains the result (e.g., positive urine test for opiates in a subject reporting use of cough syrup containing Dextromethorphan).
8. Urine pregnancy test for women of childbearing potential and discussion about study requirements regarding contraception.
9. If applicable, a discussion about study requirements regarding breast feeding.
10. Collection of venous blood for the following tests as outlined in the Schedule of Activities: hemoglobin A1C, c-peptide, complete blood count (without differential), metabolic set (including creatinine, liver set, and electrolytes), and screening for HIV, HBV and HCV ([Table 7](#)).
11. Gold scale for hypoglycemia unawareness ([Appendix 4](#)). Note: this is being collected for informational purposes only; no scores are considered exclusionary.

Once laboratory results are obtained and a final determination of eligibility is made, subjects will be contacted to schedule the first treatment visit. While immediate re-testing of laboratory results is not allowed, subjects failing to meet laboratory-based eligibility criteria may be rescreened after a 30-day wait. A single re-screening is permitted, and this re-screening is only permissible if the reason for the prior screen failure was for laboratory measurements. Blood for

clinical laboratory tests can be redrawn after a 30-day wait; however, other screening procedures do NOT need to be repeated. If the new clinical laboratory test results meet eligibility, the subject may be dosed. Otherwise, the subject is not eligible for dosing or further re-screening.

10.2. Treatment and Follow-Up Phase

Subjects will be instructed to eat normal meals during the day but to refrain from alcohol, and to follow their usual insulin regimen prior to their evening clinic arrival. Subjects will be instructed to arrive at the clinic between 6 and 8 pm on Day -1, having not had dinner.

10.2.1. Visit 2 – Treatment 1 (Day -1 and Day 1)

The following procedures will be carried out at Visit 2.

10.2.1.1. Day -1

Clinic Arrival

1. Plasma glucose (via glucose meter) will be assessed. If the result is > 350.0 mg/dL (19.44 mmol/L), no further procedures should be performed, and the visit should be rescheduled after a minimum 24-hour wait.
2. The subject will be questioned regarding any changes in concomitant medications will be documented in the eCRF, and it will be confirmed that the subject is not receiving a medication that is exclusionary.
3. Women of childbearing potential will receive a urine pregnancy test, which must be negative before further participation is allowed.

If it has been more than 30 days since Visit 1 (i.e., the visit is occurring outside of the allowed time window), venous blood will be collected for a repeat of baseline hematology and serum chemistry assessments. However, the visit may continue based on qualification at the Screening visit.

Note: At check-in for Visit 3, venous blood will be collected for a repeat of hematology and serum chemistry assessments as baseline for the first dose of study glucagon.

4. Full vital signs will be assessed after a 5-minute seated rest. It will be confirmed that the subject continues to meet eligibility requirements for SBP and DBP. Other assessments of vital signs will be made during the visit as specified in the footnotes to [Table 5](#).

Evening Meal in Clinic

1. A standardized healthy meal will be provided to the subject (see Section [7.1](#)) with a goal of completion by 9 pm.
2. The subject should follow their normal prescribed regimen for insulin per PI discretion, including meal-time correction, until midnight.

10.2.1.2. Day 1

Overnight Monitoring (starting at approximately midnight)

1. Subjects will be instructed to fast, taking nothing but water and oral glucose tablets if necessary, starting at approximately midnight and will be monitored for compliance by the CRC staff.
2. An IV catheter will be placed in one arm, maintenance fluids will be started, and the subject's insulin pump will be discontinued, if applicable. If use of an overnight IV is not possible due to site staffing considerations, use of the subject's own insulin infusion pump or SC insulin will be used overnight.
3. Plasma glucose will be monitored overnight by CGM, YSI or glucose meter; these data will be kept in the source documents. At a minimum, glucose will be assessed by BGM or YSI (not CGM) at midnight, 3 am, and 6 am; these data will be entered into the EDC. IV glucose or oral glucose tablets will be given and/or insulin will be administered by IV or infusion pump as necessary to optimize achieving plasma glucose within a target range of 80 to 150 mg/dL (4.44 to 8.33 mmol/L). If the glucose is outside the recommended target range, it will not be considered a protocol deviation.
4. Ideally, about 1 hour prior to the start of the Morning Procedures outlined below, subjects will be transitioned from SC to IV administration of insulin; any use of IV glucose will be discontinued.
5. If the subject has plasma glucose < 270 mg/dL (< 15.0 mmol/L) in the morning as measured by YSI, then the subject will be eligible to begin the Morning Procedures.

Morning Procedures (starting at approximately 6 am)

1. In the morning, plasma glucose (via YSI) will be assessed, and if > 270.0 mg/dL (> 15.0 mmol/L), the visit will be rescheduled after a minimum 3-day wait. Otherwise, the subject will be administered IV insulin to induce a baseline euglycemic steady state.
2. If not already placed, an IV catheter will be placed for administration of insulin and maintenance fluids.
3. A second IV catheter will be placed for blood sampling, ideally located in a vein within the antecubital fossa.

The hand used for blood sampling will be kept warm by use of a heated-hand box to increase blood flow and achieve "arterialized" samples. Note: The subjects will remain non-caloric fasting the morning of the procedure.

Baseline Euglycemic Steady State (early morning)

Prior to starting the hypoglycemia induction procedure, the subject must have stable plasma glucose for at least 30 minutes at 95 ± 20 mg/dL (75 to 115 mg/dL [4.17 to 6.38 mmol/L]) at a stable IV insulin infusion rate varying no more than $\pm 20\%$ during which plasma glucose must be measured at least every 15 minutes.

Hypoglycemia Induction Procedure (following baseline euglycemic steady state)

Induction Start

For the induction, the starting plasma glucose level will be determined as the average of 3 measurements taken over the final 30 minutes of the baseline euglycemic steady state period. The following procedures will then be performed:

1. Subjects will continue the IV insulin infusion at the final rate of the euglycemic steady state.
2. Subjects will be given an initial IV bolus push dose of regular insulin diluted in saline:
 - a. The dose will be calculated as 75% of the dose estimated to reduce plasma glucose from the subject's starting plasma glucose level to 54 mg/dL (3.0 mmol/L) based on the subject's self-reported glucose correction factor. This dose will be referred to as "1 bolus (full bolus dose)" subsequently.
 - b. Plasma glucose will be measured no less frequently than every 10 minutes.

The first insulin adjustment will be no earlier than 20 minutes after the initial bolus but will otherwise follow the directions for insulin adjustments shown in Section 7.2 (see also Table 4).

Insulin Dose Adjustments

Insulin dose adjustments will be performed as outlined in Section 7.2 (see also Table 4).

Randomization

Once the initial bolus dose of insulin has had time to take effect and the subjects is observed to be in a controlled rate of glucose decline, which will generally occur at approximately 30 to 60 minutes after the beginning of the induction period, the subject will be randomly assigned to receive either G-Pen or GlucaGen Hypokit in one of the treatment sequences shown in Table 3.

Confirmation of Hypoglycemic Steady State

Once the initial plasma glucose measurement < 54.0 mg/dL (< 3 mmol/L) is achieved, the IV insulin infusion will be returned to the rate established at the end of the baseline euglycemia steady state period. After 5 minutes, the IV insulin infusion will be stopped, and up to 3 confirmatory plasma glucose readings will be taken at subsequent 5-minute intervals to determine whether a hypoglycemic steady state has been reached.

A hypoglycemic steady state is defined as a confirmatory plasma glucose value ≥ 42 mg/dL (≥ 2.33 mmol/L) and < 54 mg/dL (< 3 mmol/L), and an 8-minute linearly extrapolated future plasma glucose value ≥ 42 mg/dL (≥ 2.33 mmol/L).

To determine whether a hypoglycemic steady state has been achieved, confirmatory plasma glucose measurements will be taken as necessary at 5, 10 and 15 minutes after an initial plasma glucose < 54 mg/dL (< 3 mmol/L). Depending on the outcome, the following procedures will be followed.

1. If any of the confirmatory measurements meets the criteria for hypoglycemic steady state, the subject will be eligible to receive study glucagon, and further confirmatory plasma glucose measurement are not required.

2. If the final confirmatory plasma glucose value is < 42 mg/dL (< 2.33 mmol/L), the procedure will be terminated, study glucagon will NOT be administered, and the visit will be rescheduled after a minimum 3-day wait. At the Investigator's discretion, the subject should be treated with IV glucose or oral carbohydrates, it should be verified that the subject achieved a euglycemic state and is medially stable prior to discharge.
3. If any of the confirmatory plasma glucose measurements are > 54 mg/dL (> 3 mmol/L), then the IV insulin infusion will be re-started, and insulin adjustments will be made as per the induction procedure described above (see [Table 4](#)). Once another initial plasma < 54 mg/dL (< 3 mmol/L) is obtained, the sequence of up to 3 confirmatory plasma glucose readings will be repeated.

Note: If a subject fails to achieve a hypoglycemic steady state within 60 minutes of the first plasma glucose measurement < 54 mg/dL (< 3 mmol/L), the procedure will be terminated, and the visit re-scheduled after a minimum 3-day wait.

Decision to Dose

If the subject is deemed to be within a hypoglycemic steady state, then the subject is ready to be dosed with study drug (decision to dose). At this time, the subject will be eligible to receive the randomized study drug.

Preparation and Administration of Study Drug

1. Once the induction procedure has begun and glucose < 54 mg/dL (< 3 mmol/L) is predicted to occur within approximately 1 hour, the study staff member who will be performing the study drug injection should be notified that the induction procedure is reaching conclusion. At this time the study staff member will bring the appropriate unopened test article (pouched G-Pen or Novo GlucaGen Hypokit kit) to the bedside, as assigned by the EDC system.
2. Once the hypoglycemic steady state is confirmed, the Investigator will confirm that it is appropriate to administer study drug to the subject. The clock time of this "Decision to Dose" will be captured in the source documents.
3. At this point, the subject will receive the blindfold and headphones with music playing to maintain the blind.
4. The treatment administrator will then open the study drug container (kit or pouch) and begin preparation of the glucagon for administration following the applicable IFU. An Investigator should verify that the contents of the vial of lyophilized GlucaGen Hypokit have been fully reconstituted prior to administration.
5. Subcutaneous administration of the study drug will be made to the abdomen around the umbilicus as per [Section 9.3.3](#). Clock time of study drug administration will be recorded in the source documents. After study drug injection, the study product will be disposed in a location away from the subject in a manner that maintains the blind. After disposal, the blindfold and headphones will be removed from the subject.
6. Following study drug administration, plasma glucose will be measured every 5 ± 2 minutes through 90 minutes, and every 30 ± 2 minutes thereafter through 180 minutes post-dosing.

7. At 180 minutes post-dosing, the subject will resume insulin therapy and be given a meal as per the standard practice at each site. The subject can be discharged from the clinic if their plasma glucose is >100 mg/dL (> 5.55 mmol/L) and the subject is deemed medically stable.
8. After study drug administration and before 180 minutes post-dosing, if rising glucose levels are observed and if deemed medically necessary, insulin therapy or other medical intervention may be initiated by the Investigator.
 - a. Such intervention is not recommended to occur before 90 minutes post-dosing of study drug.
 - b. Plasma glucose data and assessments of neuroglycopenic symptoms will be censored after the time of intervention, per the statistical analysis plan.
 - c. These interventions (such as insulin, carbohydrates, or a meal) prior to 180 minutes post study drug administration should be captured in the source documents, and further glucose measurements may be performed at the discretion of the Investigator.

Hypoglycemia Symptom Assessments

Subjects will complete a questionnaire regarding severity of hypoglycemia symptoms ([Appendix 1](#)) at the following time points:

1. Just before the IV bolus push dose of insulin is given at the start of the hypoglycemia induction procedure (baseline),
2. Every time blood is drawn for evaluation of plasma glucose concentration during the induction procedure,
3. Just before study drug is administered,
4. Every 5 ± 2 minutes after glucagon is administered until 90 minutes post-dosing, and every 30 minutes (coinciding with plasma glucose measurements) between 90 and 180 minutes post study drug administration.

Local Tolerability and Adverse Events

Local tolerability and AEs will be assessed as follows:

1. Subjects will complete a Visual Analog scale (VAS) questionnaire regarding injection site discomfort ([Appendix 2](#)) at 30 ± 5 , 90 ± 5 , and 180 ± 5 minutes after injection of study drug.
2. Subjects will complete an Injection Site Discomfort Description and Duration Questionnaire at 30 ± 5 minutes post-dosing. If discomfort is ongoing at 30 minutes post-dosing, the questionnaire will be updated before the subject leaves the clinic to document the final duration.
3. The Investigator will use the modified Draize scales ([Appendix 3](#)) to assess erythema and edema formation at the injection site at 30 ± 5 , 90 ± 5 , and 180 ± 5 minutes after injection of study drug. If any scores remain > 1 at the 180-minute evaluation, the subject may leave the clinic but will be instructed to contact a study staff member if the condition fails to resolve. The CRC will make every attempt to ensure that the same investigator will assess the injection sites on the subject, during both treatment visits.

Note: Even if the plasma glucose measurements have been stopped after 90 minutes, the Draize scale assessments should continue to 180 minutes post study drug injection.

4. AEs reported by the subject or observed by an Investigator during the visit will be recorded in the eCRF.

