After midnight, the Investigator should optimize plasma glucose within a target range of 80 to 150 mg/dL (4.44 to 8.33 mmol/L) through the administration of IV/SC insulin and/or IV/oral glucose. If operational considerations at a site preclude IV administration of insulin overnight, no catheter will be placed, and oral glucose tablets and the subject's own insulin infusion pump will be used to optimize blood glucose within a target range of 80 to 150 mg/dL (4.44 to 8.33 mmol/L). This range is considered a target only, and values outside of this range will not be considered protocol deviations.

In the morning of the inpatient study visit, each subject's plasma glucose will be measured and verified to be within the range of 70 to 270 mg/dL (3.89 to 15.0 mmol/L) to confirm their eligibility for continuation to the insulin induction procedure. If this criterion is not met, the visit will be rescheduled after a minimum 3 day wait.

Subjects will continue to fast during the morning of the procedure and another IV catheter for blood sampling will be inserted in their contralateral arm. Ideally, the sampling IV catheter should be placed in a vein within the antecubital fossa. The hand used for blood sampling will be kept warm by use of a heated-hand box to increase blood flow to achieve "arterialized"

samples. The subject will be kept supine and the abdomen and torso will be covered under a blanket to maintain warmth.

The baseline euglycemic steady state period will begin when the plasma glucose is confirmed to be within the range of 70 to 270 mg/dL (3.89 to 15.0 mmol/L). IV insulin will be administered to maintain the plasma glucose concentration within the range of 75 to 115 mg/dL (4.17 to 6.83 mmol/L) for 30 minutes. If the plasma glucose has been maintained within the range of 75 to 115 mg/dL (4.17 to 6.83 mmol/L) for at least 30 minutes and the insulin infusion rate varies no more than $\pm 20\%$, the induction procedure may commence.

During the induction procedure, the subject will enter a state of hypoglycemia through the administration of regular insulin diluted in normal saline (see Section 7.2), within a controlled and monitored setting. Use of the insulin dose adjustment algorithm will be facilitated by real time data capture, allowing Sponsor personnel to monitor the induction procedures virtually in real time.

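### The step-by-step visit instructions drop the 70 mg/dL floor of the morning glucose check, so a subject below 70 mg/dL is rescheduled under Protocol 7.1 but, read literally, given IV insulin under 10.2.1.2

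*Protocol*

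**What the plan says.** Protocol 7.1 (Study Overview) sets a two-sided condition. On the morning of the visit each subject's plasma glucose is to be "verified to be within the range of 70 to 270 mg/dL (3.89 to 15.0 mmol/L"), and the consequence of missing it on either side is stated: "If this criterion is not met, the visit will be rescheduled after a minimum 3 day wait". The same section repeats the range as the condition for the next step: "The baseline euglycemic steady state period will begin when the plasma glucose is confirmed to be within the range of 70 to 270 mg/dL". The synopsis also makes a subject eligible to begin the baseline period only within 70 to 270 mg/dL, but gives no reschedule rule.

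Protocol 10.2.1.2 (Day 1) states only the upper limit, twice. Overnight Monitoring step 5 opens the Morning Procedures with this condition: "If the subject has plasma glucose < 270 mg/dL (< 15.0 mmol/L) in the morning as measured by YSI". Morning Procedures step 1 reschedules if the value exceeds 270 mg/dL and continues: "Otherwise, the subject will be administered IV insulin to induce a baseline euglycemic steady state". Table 5 footnote 5 likewise reschedules only above 270 mg/dL. SAP 4.1 carries the same ceiling-only rule in its design description.

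Protocol 10.2.2 repeats the 10.2.1 procedures at Visit 3.

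**The concern.** Section 10.2.1.2 is the ordered list of actions for the treatment day. Its word *otherwise* covers every value that is not above 270 mg/dL, including values below 70 mg/dL. For those values the protocol gives two instructions that cannot both be followed: reschedule, or start IV insulin.

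Two things are at stake. One is safety: the background in Protocol 6.1.1 cites 70 mg/dL or below as the level at which patients on drug-treated diabetes should become concerned about hypoglycemia, and here it coincides with an instruction to give insulin. The other is uniform conduct: sites could act differently on the same reading, and a site that follows 10.2.1.2 to the letter would breach 7.1.

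**Working it through.** No formula or planned figure is involved, so the check sets the texts side by side and applies each to one value. The value of 62 mg/dL is illustrative and does not come from the documents.

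| Place | Condition stated | Result at 62 mg/dL |
|---|---|---|
| Protocol 7.1, morning check | 70 to 270 mg/dL, else reschedule after at least 3 days | Outside the range: reschedule |
| Protocol 7.1, start of baseline period | 70 to 270 mg/dL | Baseline period may not begin |
| Synopsis, start of baseline period | 70 to 270 mg/dL | Not eligible to begin; no reschedule rule |
| Protocol 10.2.1.2, Overnight step 5 | below 270 mg/dL | Eligible for Morning Procedures |
| Protocol 10.2.1.2, Morning step 1 | above 270 mg/dL reschedules; all others get IV insulin | IV insulin |
| Table 5 footnote 5 | above 270 mg/dL reschedules | No reschedule |
| SAP 4.1 | above 270 mg/dL reschedules; all others get IV insulin | IV insulin |

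The arithmetic is short: 70 − 62 = 8 mg/dL below the 7.1 floor, and 75 − 62 = 13 mg/dL below the lower bound of the 75 to 115 mg/dL steady state that the insulin is meant to produce. The value still satisfies below 270 and fails above 270.

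**Does any text settle the conflict?**

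- Neither 10.2.1.2 step refers back to 7.1. Cross-references are used nearby: 10.2.1.1 points to 7.1 for the evening meal, and 10.2.1.2 points to 7.2 for insulin adjustments.
- The only precedence statement in this area favors the SAP over the protocol (synopsis and 13.1). SAP section 2 confines that to statistical considerations, and SAP 4.1 omits the floor in any case.

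**What limits the consequence?**

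- Overnight step 3 requires a reading at 6 am and allows correction toward 80 to 150 mg/dL: "IV glucose or oral glucose tablets will be given and/or insulin will be administered by IV or infusion pump as necessary". It does not supply the 7.1 reschedule rule.
- Overnight step 4 works partly the other way. Ideally about 1 hour before the Morning Procedures, "subjects will be transitioned from SC to IV administration of insulin; any use of IV glucose will be discontinued".
- Before induction, "the subject must have stable plasma glucose for at least 30 minutes" at 75 to 115 mg/dL, measured at least every 15 minutes. This protects the insulin bolus, but it comes after the IV insulin step in dispute.

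**Can the number of affected visits be estimated?** No. The documents give no distribution of morning values. The planned 122 randomized subjects cannot serve as the Visit 2 denominator, because randomization follows the morning check (8.3 and 10.2.1.2), so those subjects have already passed it.

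**The case against.** The strongest reply is that the protocol should be read as a whole. The insulin in Morning step 1 is given to reach a euglycemic baseline, and 7.1 and the synopsis both say that period begins only within 70 to 270 mg/dL. A site that applies the full range satisfies every section. Insulin at 62 mg/dL would defeat its own purpose, and no careful investigator would give it. Where step 4 is followed, IV insulin is already running when the morning value is read, so step 1 adds no new exposure there.

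Much of this stands as a limit on harm. It does not remove the conflict. The step-by-step text is not silent below 70 mg/dL, because *otherwise* directs an action for every value not above 270 mg/dL. Clinical judgment might stop the insulin, but it does not tell the site whether to reschedule or to correct the glucose and continue.

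A second reply is that mandatory rescheduling costs another overnight admission, and that the sponsor might prefer to correct and recheck. That is a fair clinical preference, but rescheduling is what 7.1 already requires. If the sponsor wants the other rule, 7.1 has to change as well. Either way the sections need one rule.

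**Conclusion.** The inconsistency is real as written. It affects three protocol places (10.2.1.2 Overnight step 5, 10.2.1.2 Morning step 1, and Table 5 footnote 5) and both treatment visits. Any morning value below 70 mg/dL triggers it; no frequency can be given.

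It is a minor conduct and safety matter that should be corrected. It has no bearing on sample size, power, the primary endpoint or the analysis. The conclusion rests on a literal reading of 10.2.1.2. That sites would in fact diverge is a possibility and has not been shown.

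**What to change.** In Protocol 10.2.1.2 Overnight step 5 and Morning step 1, and in Table 5 footnote 5, state the 70 to 270 mg/dL range and the 7.1 action: if the morning plasma glucose is below 70 or above 270 mg/dL, do not start baseline IV insulin, and reschedule the visit after a minimum 3-day wait.

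Aligning the descriptive sentence in SAP 4.1 is optional and has no analytic effect. The synopsis can stay as it is. The cost is a wording change in three protocol places, with no change to design, sample size or analysis.
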